2.3. Connective Tissue Growth Factor

Connective tissue growth factor is a 38 kDa secreted matricellular glycoprotein of the cysteine-rich 61/CTGF/nephroblastoma overexpression (aka cellular communication network [CCN]) family (Perbal 2004; Rachfal 2005). It is produced by many cells, including fibroblasts, myofibroblasts, endothelial cells, mesangial cells, and stellate cells. The name “connective tissue growth factor” implies a mechanism of action similar to that of classic growth factors, which signal through specific cell-surface receptors. However, experimental evidence indicates that CTGF, and the other members of the CCN family, have activities associated with matricellular proteins that function in a more subtle modulatory fashion. Matricellular proteins are a subclass of ECM proteins that modulate cellular functions and signaling pathways through multiple mechanisms that depend on cell type and the cellular context. Prototypical representatives of this subclass include secreted protein acidic and rich in cysteine (SPARC), osteopontin, and thrombospondins (Bornstein 2002). Connective tissue growth factor fits squarely within this group of proteins, is generally expressed at high levels during development and in response to injury, and typically binds to multiple cell-surface receptors, ECM components, growth factors,

and cytokines (Chen 2009). The cellular functions that can be modulated by CTGF include secretion and/or organization of ECM, cell proliferation, survival, adhesion, migration, and epithelial mesenchymal transformation (EMT). Modulation of cellular signaling appears to occur through interactions of CTGF with 1) cell surface components such as integrins or the low density lipoprotein receptor-related protein (LRP)-1 (a multifunctional endocytic and signaling receptor), 2) cytokines and cytokine inhibitors, and 3) matrix components such as heparan sulfate proteoglycans (HSPGs) and fibronectin. Interactions with HSPGs may displace other HSPG-binding proteins such as VEGF and bone morphogenetic proteins (BMPs). Binding of cytokines to CTGF may either sequester them in an inactive conformation, or help to present cytokine binding partners to their receptors.

2.4. Connective Tissue Growth Factor in Duchenne Muscular Dystrophy

Connective tissue growth factor is a nonstructural regulatory protein present in the ECM that has an important role in fibrosis. Skeletal muscle from DMD patients, dystrophic dogs, and *mdx* mice all show elevated levels of CTGF (Porter 2003; Sun 2008).

Connective tissue growth factor can reproduce or amplify the effects of TGF- β on fibrosis by inducing collagen type 1, α 5 integrin, and fibronectin much more potently than TGF- β in fibroblasts (Kharraz 2014).

Comparison of *mdx* mice with normal or genetically depleted levels of CTGF revealed that exercised mice with reduced CTGF developed less fibrosis and exhibited better muscle strength than mice with normal levels of CTGF (Morales 2013). In culture, both myoblasts and myotubes were shown to express and secrete CTGF into the medium, and respond to the CTGF by increasing the ECM constituents, partially inhibiting myoblast differentiation and inducing myoblast dedifferentiation (Vial 2008).

In DMD, the role of CTGF might extend well beyond replacement fibrosis secondary to loss of muscle fibers, since its transient overexpression upon adenovirus injection into skeletal muscle induced a transient dystrophic-like phenotype (Morales 2011) and antibody inhibition of CTGF enabled better engraftment of satellite cells (Morales 2013).

A major manifestation of DMD is cardiac fibrosis. Cardiac fibrosis is associated with increased CTGF expression in the *mdx* mouse heart. Connective tissue growth factor may be a key mediator of early and persistent fibrosis in dystrophic cardiomyopathy (Au 2011).

Connective tissue growth factor is critically involved in several chronic fibrodegenerative diseases. Pamrevlumab treatment has been shown to positively affect the course of several of these diseases in Phase 1 and Phase 2 clinical studies.

Together, these observations suggest that CTGF may play an important role in DMD and thus, inhibition of CTGF function by pamrevlumab could result in decreased fibrosis in the muscles and possibly increased muscle function.

2.5. Clinical Trial Experience with Pamrevlumab

The clinical trial experience with pamrevlumab includes 11 clinical studies across a number of indications, including DMD that are presented in the current Investigator's Brochure.

Overall, pamrevlumab has been well tolerated. The duration of exposure by indication is displayed in the current Investigator's Brochure.

Adverse events (AEs) have been generally mild or moderate in severity and transient in duration. The AEs have been typical of the subjects' underlying medical condition(s). Infusions of pamrevlumab have been well tolerated. There is no apparent pattern to the serious adverse events (SAEs) observed during these clinical trials.

Refer to the Investigator's Brochure for additional information.

2.6. Rationale and Risk/Benefit for Pamrevlumab in Duchenne Muscular Dystrophy

Table 1: Summary of Pamrevlumab Clinical Studies in DMD

Study Number	Study Title or Description	Country	N Status	Target age of population
Duchenne Muscular Dystrophy				
FGCL-3019-079	A Phase 2, Open-Label- Study to Evaluate the Safety, Tolerability, and Efficacy of pamrevlumab in Non-Ambulatory Subjects with DMD	USA	21 Main study (Complete) OLE: (Ongoing)	12 years and older
FGCL-3019-093	A Phase 3, Randomized, Double-Blind, Trial of Pamrevlumab (FG-3019) or Placebo in Combination with Systemic Corticosteroids in Subjects with Non-ambulatory Duchenne Muscular Dystrophy (DMD)	Global	92 Ongoing	12 years and older
FGCL-3019-094	A Phase 3, Randomized, Double-Blind, Trial of Pamrevlumab (FG-3019) or Placebo in Combination with Systemic Corticosteroids in Subjects with ambulatory Duchenne Muscular Dystrophy (DMD)	Global	70 Ongoing	6 < 12 years of age

2.6.1. Rationale

The rationale and positive risk/benefit ratio for the 093 study originates in the literature and preliminary safety and efficacy data of the 079 main study, now complete. Please refer to the current Investigator's Brochure for detailed information.

2.6.2. Primary endpoint: Performance of the upper limb

Upper limb function is identified as a key priority for DMD patients' quality of life (Bergsma, 2015). The Performance of the Upper Limb (PUL) assessment was developed specifically to evaluate the wide ranging upper limb function in ambulant and non-ambulant patients with DMD (Mayhew et al, 2013). The PUL tool has been validated to provide evidence of functional progression of distal to proximal upper limb function evolution over time (Gandolla, 2020), ideal for clinical trial use.

2.6.3. Secondary endpoint: Forced vital capacity

Pulmonary dysfunction in DMD is progressive and restrictive in nature and is one of the most common causes of morbidity and mortality in non-ambulatory patients. Forced vital capacity (FVC) assessed by spirometry, is the best global assessment of all respiratory muscles, because it requires a full inspiration (reflecting function of inspiratory muscles) and a full expiration (reflecting function of expiratory muscles) (Finder, 2017). Pulmonary function tests have an excellent feasibility (defined as the percent of subjects able to perform the task) of > 95% in non-ambulatory DMD patients (Connolly, 2015). With the widespread use of corticosteroids, a delay in pulmonary function decline by 2-3 years has been observed. However, once patients are in the decline phase, a similar rate of decline has been observed regardless of glucocorticoid treatment. Several studies have shown that rates of decline are similar for both steroid- and non-steroid treated patients with DMD once in the decline phase (Mayer, 2015); (Connolly, 2015); (McDonald, 2018a).

Natural history data show that non-steroid and steroid users aged 10 to 18 years had similar changes (decline) in FVC% of 5% to 6% per year (Ricotti, 2019), (Finder, 2017), (Mayer, 2015)

2.6.4. Secondary Endpoint: Peak Expiratory Flow Rate (PEFR)

Expiratory flows are easily measured and predominantly reflect expiratory muscle function. Full inspiration is needed to achieve maximal flow; therefore Peak Expiratory Flow Rate (PEFR) requires both inspiratory and expiratory muscle function (Finder, 2017). The annual rate of change for ppPEFR was $-5.8 \pm 0.6\%/year$ (mean \pm SE) based on prospective data in DMD patients, collected in the Neuromuscular Clinic at The Children's Hospital of Philadelphia (Philadelphia, PA) from 2005–2010 (Mayer, 2015). In a more recent publication, the 1-year change in ppPEFR was -4.8% (Ricotti, 2019) with N=29.

2.6.5. Secondary endpoint: Grip Strength assessed by Hand-Held Myometry (HHM)

Preserving upper limb strength is very important in non-ambulatory DMD patients because it provides functional independence. Hand-Held Myometry (HHM) is being used in Study 079 to measure distal upper arm strength (grip and pinch strength), and it has shown very good reliability and feasibility in non-ambulatory DMD patients (Connolly 2015). A one-year follow up study in non-ambulatory DMD patients showed a mean decline in grip strength of (-3.0 newton in non-dominant arm, - 2.7 newton dominant arm) and in pinch strength (-2.2 newton in non-dominant arm, -1.7 newton in dominant arm) (Seferian 2015). In a more recent prospective natural history study (Ricotti 2019), the mean annual change from baseline (dominant arm) in Myogrip absolute value was -3.82 newton, and in Myopinch absolute value was -0.78 newton.

2.6.6. Secondary endpoint: Left ventricular ejection fraction percentage (LVEF %)

Patients with DMD, have progressive cardiac muscle dysfunction, which is the leading cause of mortality. Cardiac magnetic resonance imaging (cardiac MRI), was used to assess the left ventricular ejection fraction percentage (LVEF%) in Study 079. Care considerations for DMD (Birnkrant 2018) state that pharmacological therapy should be initiated with the onset of heart failure symptoms or when abnormalities such as depressed LVEF%, abnormal chamber dimensions, or the presence of myocardial fibrosis are noted on imaging studies (CMR or echocardiogram). Additionally, placement of an implantable cardioverter defibrillator is advised for patients with an ejection fraction of less than 35% (Epstein 2008). Based on data tracking the natural disease history, a decrease in LVEF of 0.82% per year of age (95% CI 0.94 to 0.70; $p < 0.0001$) has been observed. (McDonald 2018).

2.6.7. Forced Expiratory Volume at 1 Second (FEV1)

FEV1 assesses airway function and is the standard global assessment in both clinical and research studies of asthma, chronic obstructive pulmonary disease, and cystic fibrosis. FEV1 is understood to correlate closely with FVC, with the advantage of requiring less prolonged effort (1 second). (Finder, 2017). Data from the placebo group, in the DELOS study (Buyse, 2015) have shown that yearly rates of ppFEV1 decline were -10.2% [SD 2.0] (Meier, 2017). Cardiac fibrosis score/ Late gadolinium enhancement (LGE)

Late Gadolinium Enhancement (LGE) is a strong marker for the progression of left ventricular systolic dysfunction in DMD patients. Improvements in the cardiac function observed above are further supported by the reduction in cardiac fibrosis assessed by LGE, which is a strong marker for the progression of left ventricular systolic dysfunction in DMD patients.

Additionally, cardiac fibrosis, assessed by mass of late gadolinium enhancement (MLGE) showed a correlation between improvement in LVEF% and reduction in cardiac fibrosis, mentioned in Tandon, et al 2015 (Tandon, 2015).

2.6.8. Fibrosis and FAT assessment of the Upper Arm (Biceps brachii) assessed by MRI

In the recent years, several longitudinal studies have reported the potential value of MRI as a biomarker to assess disease progression and treatment effect in DMD. MRI biomarkers provide the advantage of studying different muscle groups in both lower and upper limbs, enabling assessment of disease progression in not only ambulant, but also non-ambulant patients incapable of performing physical tests, in addition to being an objective measure not influenced by patient's motivation during functional tests (Szigyarto 2018).

T2-mapping can help determine the level of inflammation, oedema, and fat infiltration present in the affected muscle (Magrath 2018).

Overall, the results from the completed phase 2 main study in non-ambulatory DMD subjects show that pamrevlumab may have a beneficial effect on several clinically meaningful parameters affecting the DMD population. Pamrevlumab, as an antifibrotic agent, has shown the potential to slow disease progression in patients with DMD. That, in addition to being well tolerated in pediatric patients, is considered of significant clinical benefit. Therefore, the risk-

benefit ratio remains favorable. For more information please reference the current Investigator's Brochure.

2.7. Dose Rationale Pharmacokinetics

The PK parameters of pamrevlumab have been evaluated in subjects with idiopathic pulmonary fibrosis (studies FGCL-MC3019-002 and FGCL-3019-049), subjects with pancreatic cancer (Study FGCL-MC3019-028), and subjects with diabetic nephropathy (Study FGCL-3019-MC003). PK data in DMD subjects are available from the ongoing study 079. Study results are summarized below.

2.7.1. Single-Dose Idiopathic Pulmonary Fibrosis Study FGCL-MC3019-002

Pharmacokinetics parameters of pamrevlumab were evaluated in 21 subjects receiving single dose intravenous infusions of 1, 3, and 10 mg/kg pamrevlumab over at least 120 minutes. C_{max} (µg/ml) values were: 24.58, 123.7 and 274.8 for the three doses respectively. T_{max} was 2 hours in all groups. AUC (µg.h/ml) values were: 2181, 13280 and 33190 respectively for the three doses.

Globally, the AUC and C_{max} increased with the dose over the studied dose range. The plasma elimination rate for pamrevlumab slowed with dose increase, suggesting that a saturable process may be involved in pamrevlumab elimination. Both one-compartment and two-compartment PK models adequately described the elimination phase after a single pamrevlumab infusion. The 3 mg/kg cohort exhibited a lower effective volume of distribution as a percentage of body weight, leading to a higher C_{max} than would be expected on the basis of normalized dose. This difference in the 3 mg/kg cohort may be due to the increased mean body mass index in this group (approximately 34 kg/m², compared to 29 kg/m² in other cohorts).

2.7.2. Single and Multiple-dose PK in Subjects with Incipient Nephropathy Due to Type 1 or Type 2 Diabetes Mellitus (FGCL-3019-MC003)

Single dose: The PK of pamrevlumab after administration of single doses of 3 and 10 mg/kg was evaluated in 23 subjects with incipient nephropathy due to type 1 or type 2 diabetes mellitus (PK report Study FGCL-MC3019-003). In general, the AUC and C_{max} increased more-than-proportionally to dose over the dose range in this study. Mean t_{1/2} was 73 and 141 hr at 3 and 10 mg/kg respectively. Considering the variability among the individuals and between studies, the clearance and volume of distribution values appeared to be comparable between the different subject populations at comparable pamrevlumab doses.

Multiple dose: The PK of pamrevlumab after administration of multiple IV doses of 3 and 10 mg/kg was evaluated in 18 subjects with incipient nephropathy due to type 1 or type 2 diabetes mellitus (PK report Study FGCL-MC3019-003). C_{max} at Day 0 was 72.9 ± 20.9 in the group receiving 3 mg/kg and 420 ± 211 in the group receiving 10 mg/kg. T_{max}(h) at day 0 was: 2.25 in the 3mg/kg group and 3.04 in the 10mg/kg group. Mean t_{1/2} at day 0 was 73.3±16.8 and 141±25.3 at 3 and 10 mg/kg respectively. At day 42, C_{max} values were: 76.0 ± 11.1 in the 3 mg/kg group and 511 ± 310 in the 10 mg/kg group. T_{max} values recorded at day 42 were respectively 4.12 and 6 in the two doses groups. In general, the AUC and C_{max} also increased more-than-proportionally to dose over the studied dose range. Mean t_{1/2} at day 42 was 102 and 135 hr at 3 and 10 mg/kg respectively, indicating the same trend of increasing t_{1/2} with this

comparable dose range that was observed in other studies. There was a decrease in systemic clearance values between Day 0 versus Day 42 and an increase in exposure following repeated dosing compared to the exposure after single (first) dose, which is expected based on the $t_{1/2}$ and the Q2W dosing interval. A comparison of trough levels (Day 42 versus Day 56) suggested that steady state had been reached before Day 42, which is consistent with the $t_{1/2}$ values.

2.7.3. Multiple-Dose Idiopathic Pulmonary Fibrosis Study FGCL-3019-049

Plasma PK of pamrevlumab after administration of multiple doses of 15 and 30 mg/kg every 3 weeks (Q3W) was evaluated as an exploratory endpoint in Study FGCL-3019-049 which enrolled 89 subjects with idiopathic pulmonary fibrosis. C_{max} ($\mu\text{g/ml}$) mean values reported after the 1st, 9th, and 16th doses were respectively 332 ± 85 , 349 ± 106 and 324 ± 134 at the 15 mg/kg dose. C_{max} ($\mu\text{g/ml}$) mean values reported after the 1st, 9th, and 16th doses were respectively 815 ± 219 , 860 ± 207 and 804 ± 165 at the 30 mg/kg dose. C_{min} ($\mu\text{g/ml}$) mean values after the 1st, 9th, and 16th doses were respectively 21 ± 9 , 39 ± 24 and 44 ± 24 at the 15 mg/kg dose. C_{min} mean values after the 1st, 9th, and 16th doses were respectively 99 ± 44 , 217 ± 115 and 174 ± 80 at the 30 mg/kg dose.

Overall, C_{max} and C_{min} values were consistent with those at similar time points of comparable doses in previous studies. C_{max} and C_{min} increased with increasing dose from 15 mg/kg to 30 mg/kg.

There was a general trend of increasing C_{max} and C_{min} with repeated dosing from first dose to 9th or 16th dose, which is consistent with the $t_{1/2}$ of pamrevlumab and dosing regimen of once Q3W. With a plasma $t_{1/2}$ of approximately 1 week (determined from previous studies), the steady state was expected to be reached after several doses (i.e., by the 9th dose). This is generally consistent with the observed PK data in this study. For example, the comparable mean/median C_{min} and C_{max} values at 9th and 16th doses for Cohort 2 (30 mg/kg) were slightly higher than those at Day 1. For Cohort 1 (15 mg/kg), the mean/median C_{max} values at 16th dose time point were slightly lower than those on 1st and 9th dose. However, the decrease was probably due to a reduction in the number of subjects at 16th dose time point and an increase in C_{max} variability, rather than an actual decrease in exposure over repeated dosing (from 9th to 16th dose).

PK sampling was conducted at only 2 time points (post-dose and pre-dose) between doses, so $t_{1/2}$ estimates were not available from this study.

2.7.4. Multiple-Dose Pancreatic Cancer Study FGCL-MC3019-028

In Study FGCL-MC3019-028, 75 subjects with pancreatic cancer were enrolled. Pamrevlumab was administered in combination with gemcitabine/erlotinib. Plasma PK of pamrevlumab was evaluated as a secondary endpoint after administration of multiple doses. Six cohorts were dosed at 3, 10, 15, 25, 35, or 45 mg/kg Q2W, and 2 cohorts dosed weekly at either 35 mg/kg on Day 1 followed by 17.5 mg/kg weekly or 45 mg/kg on Day 1 followed by 22.5 mg/kg weekly.

Based on the available pamrevlumab plasma-concentration data:

- C_{min} and C_{max} values increased with increasing dose. Analysis of C_{max} indicated that increases were dose proportional.
- C_{min} and C_{max} values generally increased with repeated dosing, which is consistent with the dosing regimens and $t_{1/2}$ of pamrevlumab.

- Pamrevlumab exposure (based on estimated AUC values) generally increased with increasing dose.
- Overall, C_{min} and C_{max} values were comparable to those at similar doses in previous studies.
- On Day 1, T_{max} was 3 hours from the start of dosing and 1 hour from the end of the infusion. On Day 43, T_{max} was 2 hours from the start of dosing and 1 hour from the end of the infusion.
- After the first dose, the estimated median $t_{1/2}$ increased from 2.4 days for the 3 mg/kg dose to 4.5-8 days for doses ≥ 10 mg/kg. After repeated dosing (on Day 43), the estimated median $t_{1/2}$ increased from 2.6 days for the 3 mg/kg dose to 6.6–9.0 days for doses ≥ 10 mg/kg.
- Estimated $t_{1/2}$ values for doses >10 mg/kg did not appear to increase markedly with dose, based on available data (limited time points) averaging to approximately 1 week, (the highest 2 dose regimens [35 and 45 mg/kg every two weeks] showed a median value of and 7.29 days, respectively).

2.7.5. Single Dose PK in DMD subjects in Study FGCL-3019-079

Pharmacokinetic sampling was conducted in study FGCL-3019-079, where DMD subjects were dosed with 35 mg/kg pamrevlumab once every 2 weeks. PK samples were collected predose.

<1h after end of infusion, and on Days 2, 4, 7, 10 and 14 following the first dose, as well as at steady-state at weeks 26 and 52 (predose at both times, and post dose at week 52). Pamrevlumab concentrations were measured in all plasma samples. After preliminary PK analysis (NCA) based on preliminary concentration-time profiles of each individual, the PK parameters from this study (Table 2) appeared to be comparable to those obtained from previous PK studies (study FGCL-MC3019-002 and study FGCL-3019-MC003; respectively), suggesting that the pamrevlumab exposures in pediatric DMD subjects were comparable to those in adults, without any marked exposure/PK difference between various disease of patient populations, which were shown in dose-justification analysis by population PK/PD exploration.

Table 2: PK parameters in study FGCL-3019-079 following a single dose

	T_{max} (hr)	C_{max} ($\mu\text{g/mL}$)	AUC_t (hr* $\mu\text{g/mL}$)	$AUC_{0-\infty}$ (hr* $\mu\text{g/mL}$)	$t_{1/2}$ (day)	CL (mL/hr/kg)	V_z (mL/kg)	V_{ss} (mL/kg)
Mean	2.73	970	145000	212000	8.77	0.174	52.1	50.6
SD	0.756	307	34000	49200	1.83	0.0427	15.2	14.7
Median	2.68	904	144000	215000	8.76	0.163	50.2	48.0

2.8. Safety Summary

Overall, pamrevlumab appears to be well-tolerated. As of the data cutoff date, 1723 subjects have received study drug (pamrevlumab or placebo) in the pamrevlumab clinical program including both completed and ongoing studies (1036 subjects in studies that are blinded at the time of this IB comprising 420 subjects with pancreatic cancer, 829 subjects with IPF, 112 subjects with liver fibrosis secondary to hepatitis B, 20 subjects with COVID-19, 190 pediatric

subjects with DMD, 107 subjects with DN, 2 pediatric subjects with FSGS, and 43 healthy subjects. For additional information on the safety of pamrevlumab in the completed DMD study (079) and other indications, please refer to the current version of the Investigator's Brochure.

3. OBJECTIVES AND ENDPOINTS

3.1. Objective

The overall objective of this trial is to evaluate the efficacy and safety of pamrevlumab versus placebo in combination with systemic corticosteroids in subjects with Duchenne muscular dystrophy (non-ambulatory, age 12 years and older).

3.1.1. Endpoints

3.1.1.1. Primary Endpoint

Function assessment:

- Change in the total score of Performance of Upper Limb [(PUL) 2.0 version], from baseline to Week 52.

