8. STATISTICS

8.1. Sample Size Determination

This study is planned to enroll approximately 92 subjects with a 1:1 randomization ratio of assigning to pamrevlumab and placebo, respectively. With PUL version 2.0, the sample size of approximately 92 subjects is needed to detect a treatment difference of 2.0 between treatment arms in change from baseline in the total score of PUL at Week 52, assuming a standard deviation of 2.9 with a 90% power, based on a two-sided two-sample t-test at the alpha level of 0.05.

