- f.) Full physical exam including chest auscultation
- g.) SAEs are collected from date of consent through EOS. AEs are collected from Day 0 through EOS. Number and percentage of bone fractures is captured from Day 0 through EOS. Bone fractures should be collected in the EDC as AEs, naming them using the specific guidelines in the electronic case report form completion guidelines.
- See [Section 7](#) for follow-up of AEs.
- h.) Concomitant medications and nondrug therapies must be reported beginning after informed consent is obtained and ending 60 days after the last treatment. Refer to [Section 5.2.2](#) for additional information on prohibited concomitant medications
- i.) HAHA, HAHA-NA and PK samples. See [Appendix 2](#) for PK, HAHA, and HAHA-NA sampling time points.
- j.) MFTs: Performance of Upper Limb (v. 2.0), and Hand Grip Test.
- k.) Local labs may be drawn prior to MRIs at the discretion of the investigator.
- l.) Vital signs (pulse, respiration, sitting BP, temperature) to be collected at every visit: within 30 minutes pre-infusion, and within 30 minutes after completion of infusion.
- m.) MFTs and PFTs are collected at screening and must be repeated prior to randomization and first infusion on Day 0. They may be conducted up to 3 days in advance of the Day 0 visit. The PFT results from both time points will be used to establish baseline values. The results from MFTs at Day 0 will be used to establish baseline.
- n.) Genetic Analysis samples will be collected in PAXgene tube; samples will be collected only from subjects who consent for this test. If subject consents to this optional sample, it may also be collected at an Unscheduled timepoint if it is not collected initially at Day 0.
- o.) Duchenne Video Assessment to be performed remotely within the interval between the prior scheduled study visit and next scheduled study visit.

- p.) If the subject is not going into the OLE, he should complete a final safety follow-up that consists of a visit at week 56 and a final safety follow-up phone call 60 days (+3 days) after the last infusion visit.
- q.) PFTs, MFTs, DVA and MRI only to be done at the early termination visit
- r.) Randomization may be performed within 2 days prior to Day 0 visit, after subject is confirmed eligible (see footnote “m”).

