#### 6.6.1.1.5. Population Summary for Treatment Comparison

Treatment difference of Least-square mean (LSMean) and SE at week 52 and corresponding 95% CI will be presented.

The random coefficient linear regression model (RCM), where within-patient errors follow a random coefficient regression model will be performed. The RCM model will include fixed effects of time, treatment, treatment-by-time interaction, with baseline ordinal PUL entry score as covariate. The time in the RCM model will be calculated as the elapsed weeks (considered as a continuous variable with 1 decimal place) from first dose date (or randomization date for subjects who drop out prior to any study medication) to the assessment date. All valid values including from unscheduled visits will be included.

The residual plot from the PROC MIXED output will be examined. If the residual plot shows a systematic pattern rather than a random scatter, then the linearity assumption may not be appropriate. In case of non-linearity, MMRM will be used as the primary analysis method, which is currently listed as one of the sensitivity analyses in next section.

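### PUL is scored at Screening and on Day 0, but no analysis model names the Screening score; adding both pre-dose totals as covariates would use precision already collected, though the size of the gain rests on an assumed error SD

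*Protocol*

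**What the plan says.** The primary endpoint (Protocol Section 3.1.1.1) is "Change in the total score of Performance of Upper Limb [(PUL) 2.0 version], from baseline to Week 52". Muscle function tests are PUL 2.0 and grip (Protocol Appendix 1, footnote j). Footnote m has them done at Screening and repeated before randomization and first infusion on Day 0. It then sets two baseline rules. For spirometry: "The PFT results from both time points will be used to establish baseline values". For muscle function tests: "The results from MFTs at Day 0 will be used to establish baseline". SAP Section 6.6.1 keeps the second rule for PUL, calling the day Day 1.

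The Screening score is named in no model:

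- The SAP primary random coefficient model (RCM, Section 6.6.1.1.5) has time, treatment and their interaction, "with baseline ordinal PUL entry score as covariate". Its sample code carries that entry item and no PUL total.
- The MMRM code (6.6.1.2.1.5) carries the same entry item.
- The imputation code (6.6.1.2.3.5, 6.6.1.2.4.5, 6.6.1.2.5.5) has one baseline value and Weeks 16, 28, 40 and 52.
- The protocol's primary model (Section 8.3.4.1) has one baseline PUL total.

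The stated purpose of the Screening test beyond scheduling is video quality control (Protocol Section 6.2.4). Under the general rule in SAP Section 5.3.2, a Screening score could stand in if Day 0 were missing.

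**The concern.** Every post-baseline change subtracts the same Day 0 score, so the error in that one score appears in all of a subject's changes. Later visits cannot average it out. A second pre-dose score helps to separate Day 0 error from the subject's true level, and it has already been collected.

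What is at stake is precision only; there is no question of bias or type I error. It has some weight here because SAP Section 7 accepts 87% power with 82 subjects in the mITT, against 90% in the protocol, and Protocol Section 4.5 does not replace early discontinuations.

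**Working it through.** **Inputs from the documents.** About 92 subjects at 1:1 ("the sample size of approximately 92 subjects is needed to detect", Protocol 8.1), so 46 per arm; 82 in the mITT (SAP Section 7), so 41 per arm. Difference: "needed to detect a treatment difference of 2.0 between treatment arms". Spread and power: "assuming a standard deviation of 2.9 with a 90% power". Test: "based on a two-sided two-sample t-test at the alpha level of 0.05". Visits at Weeks 16, 28, 40 and 52 (SAP Appendix 2, Table 9).

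**Assumptions, not in the documents.** The error SD *s* of one PUL total is 0.5 to 1.5 points and equal at both pre-dose visits. The between-subject SD of true baseline is 7. Baseline level is independent of later slope. Follow-up is complete.

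**Step 1: reproduce the plan's power.** Noncentral t with noncentrality 2.0 / (2.9 × √(2/n)).

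- n = 46: 2.0 / 0.605 = 3.31, 90 df, power 90.5%.
- n = 41: 2.0 / 0.640 = 3.12, 80 df, power 87.0%.

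Both agree with the stated 90% and 87%.

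**Step 2: the model.** Let T be the true level (variance 49), D = T + error the Day 0 score, S = T + error the Screening score, and Y(t) = T + bt + error a visit score, with t as a fraction of 52 weeks and each error of variance s². The Week 52 change has variance Var(b) + 2s² = 2.9² = 8.41, so Var(b) = 8.41 − 2s².

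**Step 3: why both totals are needed.**

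- Cov(Y − D, S) = 49 − 49 = 0, so Screening alone explains nothing in the change score.
- Cov(Y − D, D) = 49 − (49 + s²) = −s², so the coefficient on the Day 0 total alone is −s²/(49 + s²), or −0.02 at s = 1. It barely adjusts.
- Together they estimate T with error variance s²/2 instead of s².

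**Step 4: Week 52 ANCOVA.** With the Day 0 total, the variance is 8.41 − s² + 49s²/(49 + s²). With both totals, s²/2 replaces s² in the last term.

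- s = 0.5: 8.16 + 0.2487 = 8.4087, then 8.16 + 0.1247 = 8.2847; reduction 1.5%.
- s = 1.0: 7.41 + 0.980 = 8.390, then 7.41 + 0.495 = 7.905; reduction 5.8%.
- s = 1.5: 6.16 + 2.1512 = 8.3112, then 6.16 + 1.0998 = 7.2598; reduction 12.7%.

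**Step 5: random coefficient model.** The GLS variance v of the fitted value at t = 1 comes from the covariance matrix (8.41 − 2s²)tt′ + s²I + c11′. Here c = 49s²/(49 + s²) with the Day 0 total, and the same with s²/2 for s² with both. Power uses noncentrality 2.0/√(2v/41) and 80 df.

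| s | v, Day 0 total | v, both totals | Variance cut | Power before | Power after |
|---|---|---|---|---|---|
| 0.5 | 8.334 | 8.210 | 1.5% | 87.3% | 87.7% |
| 0.75 | 8.235 | 7.958 | 3.4% | 87.6% | 88.7% |
| 1.0 | 8.090 | 7.605 | 6.0% | 88.2% | 90.0% |
| 1.25 | 7.893 | 7.148 | 9.4% | 89.0% | 91.7% |
| 1.5 | 7.636 | 6.585 | 13.8% | 89.9% | 93.7% |

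**Step 6: sensitivity.**

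- If the Screening test has twice the error variance, the combined error variance is 2s²/3. The saving is then s²/3 instead of s²/2, one third smaller: 2.2%, 4.0%, 6.3% and 9.1% at s = 0.75, 1.0, 1.25 and 1.5.
- Over the same range of s, a baseline SD of 4 gives 3.2% to 12.4%, and 10 gives 3.4% to 14.2%.
- Two extra covariates take the 80 df to 78, which changes power by less than 0.1 point.

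**The case against.** The strongest reply is that nothing here is wrong. A last pre-dose baseline is standard and is stated consistently in both documents. That stands.

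A reader might infer an oversight from the spirometry rule in the same footnote. The documents do not support that. The averaged ppFVC is itself an entry criterion (Protocol 4.1, inclusion 8), so both sessions are needed there, whereas the PUL total is not an entry criterion. The two rules also sit side by side and look deliberate.

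The size is also open. Same-evaluator testing, proficiency checks and video review (Protocol 6.2.4) aim to keep error low, and at s = 0.5 the gain is 0.4 power points. Screening may act as a familiarisation test with larger error. A uniform practice effect goes into the intercept, but learning that varies between subjects adds noise to the covariate.

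The starting model in Step 5 is not the SAP model as written, which carries the entry item and no total, and whose sample code has a random slope without a random intercept. Nor does the calculation allow decline to vary with level, as SAP Section 7 reports it does by entry score.

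Last, the imputation text allows other baseline factors and the ANCOVA code has an open covariate slot (SAP 6.6.1.2.3.5), so Screening is unnamed but not barred. These points limit the claim. They do not remove it: the score exists and no model specifies its use.

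**Conclusion.** The point holds as an inexpensive efficiency gain and not as a defect. A pre-dose PUL score is collected on every subject and no specified model uses it. Adding it alongside the Day 0 total cuts the variance of the Week 52 RCM comparison by 1.5% to 13.8% (ANCOVA 1.5% to 12.7%) for an error SD of 0.5 to 1.5 points. That is from a negligible gain to about 4 power points.

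A reader might infer that the Screening score would restore the whole fall from 90% to 87%. The documents do not support this, because they give no figure for PUL repeatability. Modelled power reaches 90.0% only at an error SD of about 1.0 or more. Even there, part of the rise from the t-test's 87.0% comes from the repeated-visit model (88.2%), and 1.8 points come from Screening.

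The comparison should not be biased by the change. Both scores precede dosing, so an average practice effect or decline over the screening period is expected to be equal in the two arms.

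**What to change.** Amend the SAP before database lock and unblinding:

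- Keep Day 0 as the baseline for the change score (SAP 6.6.1) and the Day 0 entry item for mITT membership (5.2.2).
- Add the Day 0 PUL total and the Screening PUL total as continuous covariates in the primary RCM (6.6.1.1.5), the fallback MMRM (6.6.1.2.1.5) and the ANCOVA steps (6.6.1.2.3.5 and the analyses that refer to it). Include the Screening total in the imputation variable lists, so that the imputation model holds every analysis covariate.
- Do the same for Mid-level PUL and for grip, each with its own Screening and Day 0 values, by hand for grip.
- Where a Screening value is missing, substitute the Day 0 value.

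The cost is an SAP amendment and two model terms beyond the entry item in the primary model. The Screening term should not be added alone, because its gain depends on the Day 0 total being present. No new data are needed, and the endpoint, population and estimand are unchanged.
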